#### **9.1.2 Demographics**

Demographic information (date of birth, gender, race, and socioeconomic measures) will be recorded at Screening.

### 9.1.3 Adverse Events

Information regarding occurrence of adverse events will be captured throughout the study. Duration (start and stop dates), severity/grade, outcome, treatment and relation to study drug will be recorded on the case report form (CRF).

## 9.2 Clinical Laboratory Measurements

### 9.2.1 Urine drug testing

We will use in vitro urine drug testing for rapid, simultaneous detection of MA, amphetamine, cocaine, opioid, and MDMA in urine. At their screening visit and baseline visit (the week prior to intervention start), participants will provide a urine sample for drug testing. From Week 1 to Week 8, urine drug tests will be conducted 2x a week. One final urine drug test will be taken Week 12. Each participant will be allowed to reschedule one appointment 24 hours or more in advance, to take place within 24 hours of the original appointment. Prior to providing the urine specimen, participants empty their pockets and leave bags with a clinic staff member. To minimize attempts to provide false specimens, the participant will provide the urine sample while the pass-through specimen cabinet is open, prior to washing his hands. A temperature strip will verify the sample was provided in real-time, near body temperature.

### 9.2.2 HIV viral load

We will quantify viral load as count per milliliter of blood based on HIV RNA obtained from blood samples, and obtained at Visits B, 4.2, 8.2, and 12.0 (see Table 2). We will also compute a dichotomous variable of viral suppression, set at less than 200 c/mL.

### 9.2.3 COVID-19 immunoassay

We will conduct testing for SARS-CoV-2 (COVID-19) nucleocapsid at baseline and Visit 8.2 (Week 8) as part of health monitoring and to assess for confounding by COVID-19 infection either before or during the study.

## 9.3 Research Laboratory Measurements

### 9.3.1 Leukocyte Transcriptome Profiling – Conserved transcriptional response to adversity (CTRA)

Biomarkers of immune functioning will be measured based on leukocyte transcriptome profiling from PBMCs. To quantify abundance of genes expressed, my collaborators and I will conduct

supervised transcriptional profiling of participants from PBMCs using methods previously established and validated procedures of CTRA profiling (11, 90). Blood draws will be obtained via venipuncture at 4 visits: Baseline, Visit 4.2 (Week 4), Visit 8.2 (Week 8), and Visit 12.0 (Week 12). PBMCs will be extracted at an external laboratory and stored at -70°C. The PBMC samples will be transferred to our clinical collaborators, [name] and the UCLA Social Genomics Core Laboratory, where mRNA will be extracted using Qiagen RNeasy standard methods, converted to cDNA libraries using the mRNA-targeted Lexogen QuantSeq 3’ FWD enzyme system, and sequenced on an Illumina HiSeq 4000 instrument in the UCLA Neuroscience Genomics Core Laboratory, all following the manufacturers’ standard protocols. Sequencing will target >10 million 65 nt forward strand reads per sample, which will be mapped to the human transcriptome using the STAR aligner, quantified as gene transcripts per million mapped reads, log2-transformed for analysis, and further normalized if needed to standardize the expression of 11 pre-established housekeeping gene transcripts (91).

**10 EVALUATIONS BY VISIT**

Below is the schedule of study elements by study arm (i.e., contingency management group vs. non-substance using control (Table 3). Both groups have a screening and baseline visit.

Table 3. Schedule of study elements by study arm

Element	Visit																		
	S	B	1.1	1.2	2.1	2.2	3.1	3.2	4.1	4.2	5.1	5.2	6.1	6.2	7.1	7.2	8.1	8.2	12.0
SCID-5	▲◇																		
Screening survey and locator form	▲◇																		
Urine drug test (MA, AMP, opioids, MDMA, cannabis)	▲◇	▲◇	▲	▲	▲	▲	▲	▲	▲	▲◇	▲	▲	▲	▲	▲	▲	▲	▲◇	▲◇
Record/review HIV medications	▲◇	▲◇								▲◇								▲◇	▲◇
HIV rapid test or certification	▲◇																		
Contingent Rewards			▲	▲	▲	▲	▲	▲	▲	▲	▲	▲	▲	▲	▲	▲	▲	▲	▲
Plasma (for Viral load)		▲◇								▲◇								▲◇	▲◇
PBMC (for transcriptome profiling)		▲◇								▲◇								▲◇	▲◇

Serum (for COVID-19 immunoassay)		▲◇																	▲◇	
Behavioral survey		▲◇							▲◇										▲◇	▲◇
▲ = Contingency management (CM) for HIV-positive MSM with METH use disorder. ◇ = Non-substance-using control of HIV-positive MSM.																				

**I. Those in the Contingency Management group will have the following visit activities:**

**10.1 Screening (Visit S)**

1. Review the study with the subject and obtain written informed consent
2. Assign the subject a unique screening number
3. Screening survey (self-reported demographics, behavior, and health data) and locator form
4. Urine drug screening (participants must have a positive MA test within 30 days of this screening visit)
5. Receive certification of HIV diagnosis or HIV rapid test
6. Record HIV medications based on bottle(s) brought by participant
7. Perform SCID-5 for DSM-5 diagnosis of methamphetamine use disorder
8. Assign subject to contingency management or non-substance-using control.
9. If necessary, participants may return within 30 days to complete any screening elements if not possible to complete in the main screening visit.

**10.2 Baseline (Visit B, one week before Visit 1.1)**

1. Urine drug test
2. Behavioral survey
3. Blood draws (~50 mL total) for:
  - a. PBMCs for transcriptome profiling (~34 mL)
  - b. HIV viral load (~6 mL)
  - c. COVID-19 immunoassay (~8.5 mL)
4. HIV medications review
5. Measure weight and height
6. Record any adverse events

**10.3 Weeks 1-3 (Visits 1.1-3.2)**

1. Urine drug test
2. Contingent rewards for negative urine test

**10.4 Week 4 (Visits 4.1-4.2)**

Visit 4.1

1. Urine drug test
2. Contingent rewards for negative urine test

Visit 4.2

1. Urine drug test
2. Contingent rewards for negative urine test
3. Behavioral survey
4. Blood draws (~40 mL total) for:
  - a. PBMCs for transcriptome profiling (~34 mL)
  - b. HIV viral load (~6 mL)
5. HIV medications review
6. Record any adverse events

**10.5 Weeks 5-7 (Visits 5.1-7.2)**

1. Urine drug test
2. Contingent rewards for negative urine test

**10.6 Week 8 (Visits 8.1-8.2)**

Visit 8.1

1. Urine drug test
2. Contingent rewards for negative urine test

Visit 8.2

1. Urine drug test
2. Contingent rewards for negative urine test
3. Behavioral survey
4. Blood draws (~50 mL total) for:
  - a. PBMCs for transcriptome profiling (~34 mL)
  - b. HIV viral load (~6 mL)
  - c. COVID-19 immunoassay (~8.5 mL)

5. HIV medications review
6. Record any adverse events

**10.7 Week 12 (Visit 12.0)**

1. Urine drug test
2. Behavioral survey
3. Blood draws (~40 mL total) for:
  - a. PBMCs for transcriptome profiling (~34 mL)
  - b. HIV viral load (~6 mL)
4. HIV medications review
5. Record any adverse events

**10.8 Early withdrawal appointment**

1. Record any adverse events
2. Record reason for withdrawal if initiated by participant
3. Discuss reason for withdrawal if initiated by investigator
4. Note that participant-initiated withdrawals do not have to occur in-person, and can occur over remote communication (e.g., phone or email)

**II. Those in the Non-substance-using Control group will only have 4 visits, which will have the same components listed below:**

**10.9 Baseline, Week 4, Week 8, and Week 12 (Only control group)**

1. Urine drug test
2. Behavioral survey
3. Blood draws (~50 mL total) for:
  - a. PBMCs for transcriptome profiling (~34 mL)
  - b. Plasma for HIV viral load (~6 mL)
  - c. Serum for COVID-19 immunoassay (~8.5 mL)
4. HIV medications review
5. Record any adverse events

## 11 ADVERSE EXPERIENCE REPORTING AND DOCUMENTATION

### 11.1 Adverse Events

An adverse event (AE) is any untoward medical occurrence in a clinical investigation of a patient administered a pharmaceutical product and that does not necessarily have a causal relationship with the treatment. An AE is therefore any unfavorable and unintended sign (including an abnormal laboratory finding), symptom or disease temporally associated with the administration of an investigational product, whether or not related to that investigational product. An unexpected AE is one of a type not identified in nature, severity, or frequency in the current Investigator's Brochure or of greater severity or frequency than expected based on the information in the Investigator's Brochure.

The Investigator will probe, via discussion with the subject, for the occurrence of AEs during each subject visit and record the information in the site's source documents. Adverse events will be recorded in the patient CRF. Adverse events will be described by duration (start and stop dates and times), severity, outcome, treatment and relation to study drug, or if unrelated, the cause.

#### AE Severity

AE severity will be based on the table below.

**Table 1. AE Severity Grading**

Severity (Toxicity Grade)	Description
Mild (1)	Transient or mild discomfort; no limitation in activity; no medical intervention or therapy required. The subject may be aware of the sign or symptom but tolerates it reasonably well.
Moderate (2)	Mild to moderate limitation in activity, no or minimal medical intervention/therapy required.
Severe (3)	Marked limitation in activity, medical intervention/therapy required, hospitalizations possible.
Life-threatening (4)	The subject is at risk of death due to the adverse experience as it occurred. This does not refer to an experience that hypothetically might have caused death if it were more severe.

#### AE Relationship to Behavioral Intervention

The risk of monetary rewards exacerbating meth use disorder is unlikely because participants cannot get money unless you test negative for drugs. A participant can only get the full amount of money if they abstain for all 8 weeks, so it is unlikely that the rewards will support further drug use. This money can be used to buy essential items, things to help family and friends, and things for enjoyment like restaurant meals and movie tickets. Most people with METH dependence seek treatment to improve their lives, for themselves and for their families, and so we will help to incentivize the money to be spent on life-improving factors as opposed to drugs. There is also some risk that participants will not improve or possibly worsen during treatment, but because this is not a drug or biomedical treatment, it is difficult to attribute any adverse health events to the contingency management intervention. The relationship of an AE to the behavioral intervention should be assessed using the following the guidelines in Table 2.

**Table 2. AE Relationship to Treatment**

Relationship to Intervention	Comment
Possibly	There is no study drug. An event that follows a reasonable temporal sequence from administration of the contingency management intervention; that follows a common negative response pattern among some individuals treated with this intervention; but that could readily have been produced by a number of other factors.
Unrelated	An event that can be determined with certainty to have no relationship to the study intervention.

## 11.2 Serious Adverse Experiences (SAE)

An SAE is defined as any AE occurring at any dose that results in any of the following outcomes:

- death
- a life-threatening adverse experience
- inpatient hospitalization or prolongation of existing hospitalization
- a persistent or significant disability/incapacity

Other important medical events may also be considered an SAE when, based on appropriate medical judgment, they jeopardize the subject or require intervention to prevent one of the outcomes listed.

### 11.2.1 Serious Adverse Experience Reporting

Study sites will document all SAEs that occur (whether or not related to study drug) per UCLA OHRPP Guidelines. The collection period for all SAEs will begin after informed consent is obtained and end after procedures for the final study visit have been completed.

In accordance with the standard operating procedures and policies of the local Institutional Review Board (IRB)/Independent Ethics Committee (IEC), the site investigator will report SAEs to the IRB/IEC.

## 12 DISCONTINUATION AND REPLACEMENT OF SUBJECTS

### 12.1 Early Discontinuation of Behavioral Intervention

A subject may be discontinued from the contingency management intervention at any time if the subject, the investigator, or the Sponsor feels that it is not in the subject's best interest to continue. The following is a list of possible reasons for study treatment discontinuation:

- Subject withdrawal of consent (or assent)
- Subject is not compliant with study procedures
- Adverse event that in the opinion of the investigator would be in the best interest of the subject to discontinue study treatment
- Protocol violation requiring discontinuation of study treatment
- Lost to follow-up
- Sponsor request for early termination of study

If a subject is withdrawn from treatment due to an adverse event, the subject will be followed and treated by the Investigator until the abnormal parameter or symptom has resolved or stabilized.

All subjects who discontinue study treatment should come in for an early discontinuation visit as soon as possible and then should be encouraged to complete all remaining scheduled visits and procedures.

All subjects are free to withdraw from participation at any time, for any reason, specified or unspecified, and without prejudice.

Reasonable attempts will be made by the investigator to provide a reason for subject withdrawals. The reason for the subject's withdrawal from the study will be specified in the subject's source documents Refer to Section 10 for early termination procedures.

### **12.3 Withdrawal of Subjects from the Study**

A subject may be withdrawn from the study at any time if the subject, the investigator, or the Sponsor feels that it is not in the subject's best interest to continue.

All subjects are free to withdraw from participation at any time, for any reason, specified or unspecified, and without prejudice.

Reasonable attempts will be made by the investigator to provide a reason for subject withdrawals. The reason for the subject's withdrawal from the study will be specified in the subject's source documents. As noted above, subjects who discontinue study treatment early (i.e., they withdraw prior to Visit 5.2) should have an early discontinuation visit, especially if initiated by the investigator. Refer to Section 10 for early termination procedures. Subjects who withdraw after Visit 5.2 should be encouraged to come in for a final visit (and the procedures to be followed would include those for their next scheduled visit).

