### Protection against risks

There is minor risk that completion of survey assessments may induce distress. In such instances, participants will meet with study staff members for debriefing. The PI, [name], will keep a record of the number and type of cases that require invoking a rescue protocol and discuss these with the Medical Director, [name] and mentor [name] for participant follow-up. [name] is a licensed psychologist and will be on call in the rare case that mental health intervention is required.

There is a risk that some participants may have a MA addiction that is too severe to be adequately treated on an outpatient basis or that for any reason does not respond to the CM program. At all points during the trial participants have access to treatment facilities instead of or in addition to the CM program. Those who wish to focus solely on treatment and not on research can withdraw from study participation at any time. Any unexpected events that arise during specimen collection, survey administration, or the contingency management program that caused harm and/or that affects the risk to all participants in the research will be reported on an annual basis to the IRB.

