### **8.3 Measures of Treatment Compliance**

Treatment compliance will be based on attendance and urine drug tests, thrice weekly for 8 weeks. Each participant will be allowed to reschedule one appointment 24 hours or more in advance, to take place within 24 hours of the original appointment. Missed visits will be counted as a positive drug test. We will use the in vitro urine drug testing for rapid, simultaneous detection of MA, amphetamine, cocaine, opioids, and MDMA in urine.

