### **12.4 Replacement of Subjects**

Subjects who withdraw from the study before Visit 5.2 will be replaced.

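### Section 12.3 equates stopping contingency management early with leaving the study, while 12.1 keeps those participants in follow-up, so primary-endpoint CTRA values could go missing selectively among them

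*Combined protocol and SAP*

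**What the plan says.** Section 12.1 concerns stopping the CM intervention. Everyone who stops is to attend an early discontinuation visit, and they "then should be encouraged to complete all remaining scheduled visits and procedures". Its list of possible reasons for stopping treatment also includes withdrawal of consent and loss to follow-up, which are reasons for leaving the study.

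Section 12.3 concerns withdrawal from the study. Referring back to the preceding text, it says that "subjects who discontinue study treatment early (i.e., they withdraw prior to Visit 5.2) should have an early discontinuation visit", and it points to Section 10 for the procedures. For later departures it says: "Subjects who withdraw after Visit 5.2 should be encouraged to come in for a final visit", with the procedures of the next scheduled visit.

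Section 10.8, the early withdrawal appointment, covers adverse events and the reason for withdrawal. It lists no blood, urine or survey collection. If the participant initiates the withdrawal, the contact may be remote.

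Section 12.4 states: "Subjects who withdraw from the study before Visit 5.2 will be replaced".

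CTRA and viral load are both measured at Visits B, 4.2, 8.2 and 12.0 (Sections 9.2.2 and 9.3.1). Section 15.1 defines a safety population and no efficacy analysis set.

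**The concern.** Stopping CM and leaving the study are different events. A participant may stop CM and still be willing to give blood at Weeks 4, 8 and 12. Section 12.1 provides for that person. The parenthesis in 12.3 makes early treatment discontinuation the same thing as withdrawal, and no passage says which section governs.

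The choice matters because of who is affected. The primary analysis compares CTRA trajectories between the groups (15.3), and the association model relates CTRA to the methamphetamine urine result across the four blood-draw visits (15.6). Participants who stop CM may well differ from those who stay, both in methamphetamine use and in CTRA. If their blood draws end when CM ends, the CM trajectory increasingly describes those who remained in CM. The rule in 8.3 that a missed visit counts as a positive urine test does not help, because it supplies no CTRA value. Replacement under 12.4 could then bring the head count back to target while the people who stopped drop out of view.

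**Working it through.** **Reading the sections together.** Take a participant who stops CM in Week 3 and has not withdrawn consent.

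- Under 12.1 he has a discontinuation visit and is encouraged to attend the rest. CTRA is scheduled at 4.2, 8.2 and 12.0.
- Under the wording of 12.3 he counts as having withdrawn before 5.2. He is sent to 10.8, which has no blood draw, and 12.4 replaces him. No further CTRA is scheduled.

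**The plan's own count.** Inputs from 15.7 and 4.1: 55 participants (35 CM, 20 control), 4 measurements each, 80% retention.

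- 55 × 4 = 220
- 220 × 0.80 = 176

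Both figures reproduce. The stated minimums are 135 (linear models) and 154 (logistic model).

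**Values at stake per participant.**

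- Stops before 4.2: Weeks 4, 8 and 12, so up to 3.
- Stops after 4.2 but before 5.2: Week 4 already exists, so up to 2.
- Leaves after 5.2: the final visit in 12.3 includes CTRA only if the next scheduled visit is 8.2 or 12.0.

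**Range.** The documents do not say how many will stop CM, so I assume 10% to 50% of 35. With k stoppers, no replacement and no other loss, the remaining total is 220 − 3k (stop before 4.2) or 220 − 2k (stop between 4.2 and 5.2). Post-baseline CM values planned: 35 × 3 = 105.

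| k of 35 | 220 − 3k | Share of 105 lost, 3k/105 | 220 − 2k |
|---|---|---|---|
| 4 | 208 | 11% | 212 |
| 7 | 199 | 20% | 206 |
| 10 | 190 | 29% | 200 |
| 14 | 178 | 40% | 192 |
| 18 | 166 | 51% | 184 |

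**Against the plan's figures.** With 3 values lost each, the total stays at or above 176 for up to 14 stoppers (220 − 42 = 178), at or above 154 for up to 22 (220 − 66 = 154), and at or above 135 for up to 28 (220 − 84 = 136).

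**What replacement does.** With k = 7 and each replacement giving 4 values, the total is 199 + 28 = 227 if the stoppers' baseline values are kept, or 220 − 28 + 28 = 220 if they are discarded. Either way the count looks complete, although the 21 post-stopping values (7 × 3) are still absent.

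**The case against.** The strongest reply is that 12.3 can be read in harmony with 12.1. Its sentence refers back to the earlier text, repeats the discontinuation visit and never revokes the encouragement to complete later visits. The section headings also separate stopping the intervention from leaving the study. This stands to a degree: the documents do not say that follow-up ends when CM stops, and a reader who infers that 12.3 requires it goes too far. But the parenthesis, the heading of 12.3, the content of 10.8 and the replacement rule all point a site towards treating the participant as withdrawn, so the ambiguity remains. It is also true that encouragement under 12.1 does not guarantee attendance, so 3 values per person is a maximum.

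Several stronger readings are tempting and are not supported.

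- *Continued methamphetamine use is a ground for stopping CM.* The listed reason in 12.1 is "Subject is not compliant with study procedures", whereas 8.3 says "Treatment compliance will be based on attendance and urine drug tests". Giving a sample is the procedure, and a positive result is not a failure to perform it. Section 8.2 handles relapse within CM through the reward reset. Participants who keep using can therefore remain in CM and contribute positive observations.
- *Section 12.1 is unworkable because the remaining visits carry rewards.* Someone discontinued from CM can naturally be understood as no longer offered them, though the text does not say so.
- *People who move to other care are lost through this wording.* The part of Section 2.1 on protection against risks says "At all points during the trial participants have access to treatment facilities instead of or in addition to the CM program", so other care need not replace CM. It then says separately that those wanting treatment only may leave the research. Those people choose to leave.
- *The study becomes too small.* The counts above do not show this, and under 12.4 the lost observations may be made up by new participants.

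**Conclusion.** The conflict is in the text and should be resolved. A site following the wording of 12.3, 10.8 and 12.4 could end CTRA and viral-load collection in participants who have stopped CM but would still attend, and then replace them.

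Up to 3 values per person are at stake for a stop before 4.2, and up to 2 for a stop between 4.2 and 5.2. Over the assumed range of 4 to 18 early stoppers, 11% to 51% of the planned post-baseline CM values depend on which section is followed. These are upper limits: they assume full attendance under 12.1 and none under 12.3.

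The consequence is selective missingness of the primary endpoint, with replacement hiding the selection. Neither stated minimum is missed within that range when CM stopping is the only source of loss, although at 18 stoppers the total of 166 falls below the 176 expected at 80% retention. The plan does not say how much of its 44-observation allowance (220 − 176) is meant for CM stopping. The size and direction of any bias cannot be computed, because the documents give no stopping rate and no expected CTRA difference between those who stop and those who stay.

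**What to change.** Reconcile 12.1, 12.3, 12.4 and 10.8 as follows.

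1. Delete the parenthesis in 12.3 that equates early treatment discontinuation with withdrawal before Visit 5.2.
2. Record stopping CM and withdrawing from the study as separate statuses, each with its own date. The reasons listed in 12.1 should be sorted accordingly.
3. State that stopping CM alone does not end the assessments already scheduled. At minimum, blood, urine and survey at 4.2, 8.2 and 12.0 should continue for those willing. The other scheduled urine tests need not be dropped, since they inform the negative-urine endpoint.
4. Apply 12.4 replacement only to withdrawal from the study, and keep replaced participants' data in the analysis.

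The grounds for stopping CM, the grounds on which the investigator or sponsor may withdraw a subject, and whether rewards apply at visits after CM stops are for the sponsor to reconcile.

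The cost is wording changes in these sections and two CRF fields. No visit is added beyond those already scheduled, and the assessment visits are already compensated in Table 2 of Section 8.2. The downside is staff time to retain people who have stopped CM. The change should be made early, because blood that was not drawn cannot be recovered.
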